As Vapotherm Hi-VNI technology becomes more common-place in hospital standard of care & practice, HVNI therapy may also have a demonstrable effect on improving patient ambulation and mobility. Mobility represents a key factor in the timely improvement of patient health, and in end-of-life cases it can have a mental impact⁸. In addition to the patient benefits, ambulation and early ambulation & mobility can also reduce the patient hospital resource allocation and reduce the length of stay (LOS). Some hospitals have included patient ambulation metrics as a key success factor, and this also can play a role to stepping-down

Vapotherm, Inc

HVNI Ambulation Feasibility Study

Confidential

the patients to less critical care environments. The goal of this study is to establish a low risk model, modified from the 6MWT, for patients with dyspnea: (1) evaluate the effect of HVNI on ambulation, and (2) assess the impact HVNI use may have on improved outcomes when compared to standard TAU (HVNI).

Vapotherm, Inc
HVNI Ambulation Feasibility Study
Confidential

II. Overall Study Objective

The **overall objective** of this study is to evaluate the ability of HVNI to improve patient ambulation relative to a treatment as usual (TAU).

The **hypothesis** is that HVNI therapy, when implemented in conjunction to ambulatory practices, will be more effective than TAU to improve patient mobility by reducing the patient's perceived dyspnea and exertion via maintaining oxygenation (reduced desaturation) and supporting ventilation (reduced work of breathing [WOB]).

To test this hypothesis, the study will be conducted with the following specific aims:

Aim #1: Primary Outcome. The primary endpoint is exercise performance, defined as the distance and duration of patient ambulation.

Aim #2: Secondary Outcomes. The secondary endpoints evaluate the patient recovery interval, defined as the recovery time (return time to baseline perceived dyspnea). Other endpoints will include: vital signs (heart rate [HR], respiratory rate [RR], blood pressure [BP]), arterial oxygen saturation (SpO₂), rated perceived exertion (RPE), and rated perceived dyspnea (RPD).

Aim #3: Tertiary Outcomes. The tertiary endpoints evaluate the clinician perception scores. For the clinician perceptions this will include: technical/clinical difficulties, patient comfort & tolerance, ease of use, monitoring & support for therapy, and expected/perceived patient outcomes.

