This will be a feasibility study, performed as a prospective, crossover trial to evaluate the potential patient improvement during ambulation while on HVNI relative to TAU. Patients who fit the criteria for inclusion will perform ambulation for each study period: the baseline period (TAU) followed by the test period (HVNI). The clinical management will otherwise remain unchanged based on the site SOC practices. The patient FiO_2 and flow values will be recorded while on any supplemental oxygen. Subjects will wear appropriate gear and, when applicable, have mobile carts to provide supplemental oxygen therapy (e.g. HVNI VTU) during ambulation.

This feasibility study design focuses on three distinct phases: (1) baseline characterization, (2) performance measures of ambulation, and (3) clinician perceived satisfaction scores. The baseline characterization is to provide patient background, history, and initial relevant clinical evaluation from Aim 2. Performance

Vapotherm, Inc

HVNI Ambulation Feasibility Study

Confidential

measures from Aims 1 & 2 will provide physiologic relevant indices before/during/after ambulation session and will be used for meaningful comparison between study arms. Lastly, Aim 3 will provide an overall assessment from the clinician perceived satisfaction scores.

This feasibility study will involve two study periods: baseline (TAU) and test (HVNI). Baseline period will be administered first, followed by the test period. Patients deemed in need of ambulation (per inclusion/exclusion criteria) will be enrolled into the study and will complete both study periods:

1. Treatment as usual (TAU) of standard practices (control arm) for ambulation at site
2. Vapotherm HVNI therapy (test arm) administered as described below during ambulation at site

This feasibility study will be conducted in a research facility and where testing can be performed with appropriate supervision and staff training to maintain patient safety. This current study uses a modified 6MWT ambulation test to evaluate the patient performance. Primary and secondary outcomes will be completed upon the completion of each study arm's ambulation test. Tertiary outcomes will be completed upon study. All respiratory interventions will be tracked during the study window, and disposition and mortality will be tracked for each patient.

V. Subject Enrollment

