Upon enrollment, appropriate study data will be collected (see below under Data Collection), including patient demographics, anthropometrics, and applicable history (LTOT user, positive-airway pressure therapy user, current respiratory therapy). Subjects will be managed by routine care while study data is captured as shown in the timeline below (Table 1). All decision making for patient ability to ambulate and continue study procedures will be made per standard practice at the site, using the judgment of the research team.

[figure not shown]

Figure 1. Framework of the clinical study procedures discussed within this protocol.

Vapotherm, Inc

HVNI Ambulation Feasibility Study

Confidential

Control Session

The Control session is treatment as usual (TAU), without use of HVNI during any time of this study period.

The Control session will follow three phases (see Figure 1 & Table 1): Baseline Characterization, Ambulation Test, and Recovery Interval. After these phases are complete, the next ambulation exercise will be determined per standard practice and when deemed appropriate by investigator.

Prior to the Control Session baseline characterization, the subjects should wear comfortable clothing, appropriate walking shoes, and usual walking aids (cane, walker, etc.). No vigorous exercise should be performed 2 hours prior to the ambulation test³³.

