Baseline Characterization Sitting down, the subject will be setup and prepared for the ambulation test with appropriate data recording devices and supplemental oxygen (not HVNI). The subject will be allowed to acclimate to the supplemental oxygen during this period of time. While subject is at rest, standing up, the following data will be collected (see Table 1): RR, HR, BP, SpO₂, and RPD (Modified Borg scale 0-10). For the RPD & RPE, the coordinator will record patient scores, the FiO₂ and flow settings for any supplemental oxygen provided to the patient before/during/after this baseline phase. TAU will not include HVNI in this study period. The Ambulation Test will be performed after the baseline characterization is. The definition for this ambulation test will be to walk until 18 minutes has elapsed or the patient is unable to continue. A timer will keep track of the test duration, and the clinician will keep track of the distance traveled during ambulation. At test start, test end, & 1-minute intervals the subjects will be asked to rate their RPE (Modified Borg scale 0-10). The subject vitals will be monitored during this ambulation test and recorded as follows: HR, RR, SpO₂. The ambulation test will end if the subject has completed 18 minutes, stops walking for more than 10 seconds, has to sit down, has any adverse events, or should the investigator deem necessary.

Recovery Interval will begin immediately following the end of the Ambulation Test. The subject will perform this recovery interval while safely seated. The time to return to the subject's resting-while-standing RPD score (Baseline) will be used as recovery time. At the end of the recovery interval, record the subject RR, HR, BP, SpO₂, and RPD & RPE. Any adverse events will be recorded. Any exacerbations from ambulation walk test will be recorded during the recovery interval. Record the recovery end time and date.

After the Recovery Interval is complete, all associated data will be collected including clinician perception/satisfaction scores. Then the study will pause until the next ambulation test is scheduled. The next ambulation test will be determined per standard practice and when deemed appropriate by the investigator.

Test Session

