Baseline Characterization will be performed just prior to the next scheduled ambulation test, as deemed appropriate for the patient by the investigator. Sitting down, the subject will be setup and prepared for the ambulation test with appropriate data recording devices and supplementary oxygen (only HVNI). While subject is at rest, standing up, the following data will be collected (see Table 1): RR, HR, BP, SpO₂, and RPD (Modified Borg scale 0-10). For the RPD & RPE, the coordinator will record patient scores. Record the FiO₂ and flow settings for any supplemental oxygen provided to the patient before/during/after this baseline phase.

The Ambulation Test will be performed after the baseline characterization is complete, and in accordance to the standard practice of the site and judgment of the investigator to maintain patient safety. The definition for this ambulation test will be to walk until 18 minutes has elapsed or the patient is unable to continue. A timer will keep track of the test duration, and the clinician will keep track of the distance traveled during ambulation. At test start, test end, & 1-minute intervals the subjects will be asked to rate their RPD & RPE (Modified Borg scale 0-10). The subject vitals will be monitored during this ambulation test and recorded as follows: HR, RR, SpO₂. The ambulation test will end if, the subject has completed 18 minutes, stops walking for more than 10 seconds, has to sit down, has any adverse events, or should the investigator deem necessary.

Recovery Interval will begin immediately following the end of the Ambulation Test. The subject will perform this recovery interval while safely seated. The time to return to the subject's resting-while-standing RPD score (Baseline) will be used as recovery time. At the end of the recovery interval, record the subject RR, HR, BP, SpO₂, and RPD & RPE. Any adverse events will be recorded. Any exacerbations from ambulation walk test will be recorded during the recovery interval. Record the recovery end time and date.

After the Recovery Interval is complete, all associated data will be collected (per Table 1). This includes all end-of-study data prior to study completion including perception/satisfaction scores.

Other Medical Care

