All other pharmaceutical and medical treatment will remain the purview of the attending physician and will be administered per the current standards. This study is designed to evaluate only intervention of HVNI in conjunction with standard (TAU) ambulatory practice, and it is assumed that the ancillary interventions will

Vapotherm, Inc
HVNI Ambulation Feasibility Study
Confidential

follow common clinical practice guidelines and conventions. All treatments given to the subjects will be noted on their CRFs.

VapoTherm, Inc
HVNI Ambulation Feasibility Study
Confidential

VII. Data Collection

Table 1. Key study data and collection points.

	Baseline Characterization	Ambulation Test	Recovery Interval	@ Study End
Patient History & Health	X			X
Treatment: Flow & O2	X	X	X	X
Physiologic Parameters	X	X	X	X
Performance Parameters		X		
Recovery Parameters			X	
Clinician Perception Scores			X	X
Disposition	X			X

Patient enrollment data collection will include patient history, health, demographics, and interventions. For each test session the following data will be recorded for comparison.

Physiologic Parameters

- SpO₂, HR, RR, BP, RPE, RPD

Performance Parameters

- Test duration and test distance traveled

Recovery Parameters

- Return time to baseline RPD, HR, RR, BP, SpO₂, RPD, RPE

Primary Endpoint

- Distance and duration of exercise during ambulation

Secondary Endpoints

- Physiologic parameters – SpO₂, HR, RR, BP, RPE, RPD
- Recovery parameters: return time to baseline Rated Perceived Dyspnea score
- Modified Borg scale scores – Rated Perceived Exertion (RPE), Rated Perceived Dyspnea (RPD)

Tertiary Endpoints

- Clinician perception of patient respiratory response to therapy, ranging from NO Response to Excellent Response, as continuous VAS.
- Clinician perception of frequency of rain-out, interface slippage or other technical/clinical difficulties applying therapy, ranging from Never to Frequent as continuous VAS.
- Clinician perception of patient comfort and tolerance of therapy, ranging from Very Poorly Tolerated to Very Well Tolerated as continuous VAS.

Vapotherm, Inc

HVNI Ambulation Feasibility Study

Confidential

- Clinician perception of Simplicity of set-up and use, ranging from Complex to Setup and Use to Simple to Setup and Use, as continuous VAS.
- Clinician perception of Monitoring and support of therapy required (adjustments, refilling fluids, adjusting interface), ranging from Almost Constantly to Almost Never, as continuous VAS.

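### The control walk asks for exertion ratings only, while the HVNI walk asks for dyspnea and exertion, so in-walk dyspnea cannot be paired if the procedures are followed as written

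*Combined protocol and SAP*

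**What the plan says.** Section VI describes the two walks in nearly identical text, with one difference in the ratings.

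- **Control Session, Ambulation Test:** "At test start, test end, & 1-minute intervals the subjects will be asked to rate their RPE (Modified Borg scale 0-10"). The other in-walk measures are HR, RR and SpO₂.
- **Test Session, Ambulation Test:** at the same time points, "the subjects will be asked to rate their RPD & RPE (Modified Borg scale 0-10"). The other in-walk measures are again HR, RR and SpO₂.

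Section VII, Data Collection, marks the physiologic parameters category for the Ambulation Test column of Table 1. The list below the table puts both RPE and RPD in that category, introduced by "For each test session the following data will be recorded for comparison". Section VI, under Screening, Enrollment, & Management, says that "study data is captured as shown in the timeline below (Table 1").

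Section II states the hypothesis that HVNI improves mobility by reducing "perceived dyspnea and exertion via maintaining oxygenation" and supporting ventilation. Aim #2 names among the secondary endpoints "rated perceived exertion (RPE), and rated perceived dyspnea (RPD"). Section VIII plans a Wilcoxon signed-rank test on all applicable variables, which needs a value from each session for each subject.

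**The concern.** Dyspnea during the control walk is required by one part of the protocol and left out of the instruction that staff would use while running that walk. If they follow the instruction, exertional dyspnea is measured on one side of the pair only, and the dyspnea part of the hypothesis cannot be tested within patient during exercise.

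Recovery time is affected less directly. It is the time to return to the standing-rest RPD and stays measurable in both sessions. But "Recovery Interval will begin immediately following the end of the Ambulation Test", and the control text does not ask for RPD at that moment. The HVNI recovery time would have a recorded starting dyspnea and the control one would not, so a shorter recovery on HVNI could not be separated from a lower dyspnea at the end of the walk.

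**Working it through.** The plan gives no figure for this point that could be reproduced. The check is a comparison of texts, a count, and one illustration of precision.

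**1. RPD in each session, following Section VI literally**

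| Time point | Control (TAU) | HVNI | Pairable? |
|---|---|---|---|
| Standing rest, before the walk | RPD | RPD | Yes |
| Walk: start, each minute, end | RPE only | RPD and RPE | RPE yes, RPD no |
| End of recovery | RPD and RPE | RPD and RPE | Yes |
| Recovery time | Return to resting RPD | Return to resting RPD | Yes |

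The pairable RPD values do not replace the in-walk ones. Standing rest precedes exercise. End-of-recovery RPD should equal baseline by construction, because recovery is timed to the return to baseline RPD.

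**2. Does Table 1 supply the missing instruction?** Only in part. It names a category, has no split by session and gives no frequency. Nor is the mark a reliable guide item by item: BP is in the same list, yet neither walk text records it. The sentence on RPD and RPE in the control baseline paragraph concerns the baseline phase, not the walk.

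**3. Count of ratings.** For a walk of *m* whole minutes, with the end rating falling on the last minute, the number of ratings is *m* + 1.

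- 18 minutes (the maximum in Section VI): 18 + 1 = 19.
- 6 minutes: 6 + 1 = 7.
- Control in-walk RPD: 0 in either case.
- Ceiling for 26 subjects (the calculated sample size in Section V): 26 × 19 = 494 HVNI ratings without an in-walk control counterpart.
- If standing-rest RPD is accepted as a stand-in for the start rating: 26 × 18 = 468.

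Both totals assume that every subject walks the full 18 minutes. Ratings within a subject are repeated measures, so the relevant loss is in subject pairs: 0 of 26 available under the literal reading, and up to 26 if RPD is collected as Section VII implies.

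**4. If practice is mixed.** Some staff may follow the walk text and others Table 1. The shares below are assumptions; the documents give none. The detectable standardized paired difference *d* (mean difference divided by the SD of differences) solves P(T > t₀.₉₇₅, n−1) = 0.90, where T is noncentral t with n − 1 degrees of freedom and noncentrality d√n. For the signed-rank test, n is replaced by n × 3/π.

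| Control walks omitting RPD (assumed) | Pairs | d, paired t | d, signed-rank (approx.) |
|---|---|---|---|
| None | 26 | 0.66 | 0.68 |
| About a quarter | 20 | 0.76 | 0.78 |
| Half | 13 | 0.98 | 1.01 |
| All | 0 | none | none |

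The plan sets no effect size or power target for RPD, and N = 26 is justified by walking distance. The table therefore shows only how precision falls with lost pairs.

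**The case against.** The strongest reply is that the protocol already covers this. Section VI ties data capture to Table 1, Section VII applies the RPD-containing category to each session, Section XI provides for regular monitoring, and Section XII counts failure to record protocol data as a deviation. On that view harm arises only if staff follow the walk text over Table 1 and monitoring misses it. This softens the problem without removing it. Table 1 gives no minute-by-minute schedule, and a monitor checking against the control-walk text would find nothing missing.

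Several narrower points stand in whole or in part:

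- The start-of-walk rating has a close counterpart in standing-rest RPD, so about 18 ratings per subject, not 19, lack any match.
- The total of 494 is a ceiling. Subjects with GOLD 4 disease, or GOLD 3 with significant exertional dyspnea, may well stop before 18 minutes.
- The precision figures rest on assumed omission shares and add little to the textual finding.
- Recovery time as defined does not use a starting RPD, and no planned analysis relates the two. The effect is on interpretation, not on whether the endpoint can be computed.
- Session order is a minor matter, since a rating that is not asked for is lost in either order. The protocol states "Baseline period will be administered first, followed by the test period", so an omission noticed only when RPD is asked for on HVNI is noticed after that subject's control walk is over.

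None of these explains why the two walk instructions differ.

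**Conclusion.** The concern holds. The control-walk instruction is wrong as written: it conflicts with the HVNI-walk instruction and with Section VII, and it leaves a named secondary endpoint without an in-walk control value. Under the literal reading there are 0 in-walk RPD pairs among 26 subjects, with 0 control ratings against up to 19 on HVNI in a full-length walk. If staff collect RPD from Table 1 instead, up to 26 pairs exist, at an unstated frequency.

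Confidence is high that the texts conflict. Whether data would be lost is uncertain, because the case report form is not in the documents and the omission may be a drafting slip. Distance, duration, in-walk RPE and recovery time can still be compared. The point should be fixed, but it does not threaten the primary result.

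**What to change.** - **Section VI, Control Session, Ambulation Test:** ask for RPD as well as RPE, at test start, each minute and test end, matching the Test Session.
- **Section VII:** add one line stating that RPD and RPE are recorded at those times in both sessions, so that the two walk texts and Table 1 agree. Check that the case report form has the same fields for both walks.
- **Optional and separate, Section VIII:** because walk durations may differ between sessions, a comparison of RPD and RPE at the last minute reached in both could be added. The inconsistency can be resolved without it.

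The cost is a two-word edit, one clarifying sentence, and one extra 0–10 question at each rating time in the control walk, at most 19 per subject. No visits, equipment or subjects are added.

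### Recovery vitals and Borg scores are scheduled only at the moment dyspnea returns to baseline, so recovery RPD is fixed by definition and the vitals are not compared at matched times

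*Combined protocol and SAP*

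**What the plan says.** Section VI (Study Procedures) gives the same recovery rule for the Control and Test Sessions.

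- Start: "Recovery Interval will begin immediately following the end of the Ambulation Test".
- Posture: "The subject will perform this recovery interval while safely seated".
- Recovery time: "The time to return to the subject's resting-while-standing RPD score (Baseline) will be used as recovery time".
- Readings: "At the end of the recovery interval, record the subject RR, HR, BP", together with SpO2, RPD and RPE.

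The text schedules no recovery reading at a fixed elapsed time. It gives no interval for asking RPD while its return is awaited, no maximum duration, and no rule for a subject whose RPD does not return.

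During the walk, Section VI lists HR, RR and SpO2, plus RPE each minute; RPD each minute is listed for the Test Session only. Table 1 in Section VII marks physiologic parameters, a group that includes BP, for the walk.

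Section VII says the session data are recorded for comparison. Its recovery parameters begin "Return time to baseline RPD, HR, RR, BP" and go on to SpO2, RPD and RPE. The secondary endpoints name only the RPD return time as a recovery endpoint, and list the physiologic parameters with no time point. Section VIII applies a Wilcoxon signed-rank test at 0.05 to every variable to which it applies.

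**The concern.** The moment of reading is set by another secondary endpoint. Two consequences follow.

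First, RPD at the end of recovery is the value that ended recovery. Testing it between sessions only repeats the difference between the two baseline RPD scores.

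Second, HR, RR, BP, SpO2 and RPE are read at each session's own recovery time. The hypothesis in Section II is that HVNI reduces perceived dyspnea. If it also shortens dyspnea recovery, the two readings in a pair fall at different points on the recovery curve, and the comparison mixes how far the vitals have recovered with how long they were given. A difference can appear where there is none, and a real one can vanish. Section V says the data are to inform a follow-on randomized study, so an uninterpretable recovery comparison could carry forward into its design.

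**Working it through.** The plan gives no figure on this point, so there is nothing to reproduce. The structural part is a reading of the text; the size is an illustration.

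**Structure.** Recovery starts at walk end and stops when RPD reaches its baseline score. Hence elapsed time at the reading = that session's RPD return time, and RPD at the reading = that session's baseline RPD. Coarse polling, or sitting in recovery against a standing baseline, allows only small departures from equality.

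**Illustration.** None of these inputs comes from the documents:
- HR excess over rest at walk end: 30 bpm in both sessions, decaying as 30 × exp(−t/τ)
- RPD return: 5 min on TAU, 3 min on HVNI
- τ on TAU: 1, 2 or 4 min

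Reported difference (HVNI − TAU) = 30 × exp(−3/τ_HVNI) − 30 × exp(−5/τ_TAU). For τ_TAU = 2:

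1. Identical HR recovery (τ_HVNI = 2): 30 × exp(−1.5) − 30 × exp(−2.5) = 6.7 − 2.5 = +4.2 bpm.
2. HR recovery faster in proportion to dyspnea (τ_HVNI = 2 × 3/5 = 1.2): 30 × exp(−2.5) − 30 × exp(−2.5) = 0.0 bpm. Read at 3 min in both sessions, HVNI would be lower by 6.7 − 2.5 = 4.2 bpm, so a real benefit is reported as zero.
3. HR recovery faster still (τ_HVNI = 0.4 × 2 = 0.8): 30 × exp(−3.75) − 30 × exp(−2.5) = 0.7 − 2.5 = −1.8 bpm. Read at 3 min in both, the difference would be 0.7 − 6.7 = −6.0 bpm.

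| τ on TAU (min) | Identical | Proportional | τ_HVNI = 0.4 × τ_TAU |
|---|---|---|---|
| 1 | +1.3 | 0.0 | −0.2 |
| 2 | +4.2 | 0.0 | −1.8 |
| 4 | +5.6 | 0.0 | −4.0 |

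In this model the session with the quicker dyspnea recovery reads lower only if τ_HVNI/τ_TAU is below the ratio of the reading times (here 3/5 = 0.6). With identical curves and the same three values of τ, reading times of 3 vs 4, 2 vs 4 and 2 vs 6 min give +0.9 to +11.5 bpm.

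**What the model leaves out.** The walk lasts "walk until 18 minutes has elapsed or the patient is unable to continue", so exercise before recovery, and HR at walk end, can differ between sessions. Only HR is modelled; nothing here sizes the effect on RR, BP, SpO2 or RPE.

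**The Section VII list.** If the recovery-parameter line means a return time for every variable, one recorded reading per session cannot supply them. If it means RPD return time plus values at that moment, the timing problem above applies.

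**The case against.** The strongest reply concerns direction. A reader might infer that the rule penalises whichever session recovers faster, and so works against HVNI. The documents do not support that as a general statement. The hypothesis is that dyspnea falls because oxygenation is maintained and ventilation supported, so the vitals may well recover faster too, and the reported difference can then be zero or favour HVNI. This stands. Every bpm figure also rests on assumed inputs.

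It can also be said that the only named recovery endpoint is the RPD return time, which this rule does not harm, and that HR, RR and SpO2 are recorded during the walk, closer to exertion. That stands and limits the impact. It does not remove the problem: the end-of-recovery readings are listed as recovery parameters for comparison, and Section VIII does not exclude them from testing.

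A reader might further infer that BP is never measured near exertion. The Section VI text suggests this, but Table 1 marks physiologic parameters for the walk. It is an inconsistency to reconcile, not proof that BP is omitted.

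Recording RPD at the end of recovery usefully documents the stopping event; the objection is only to testing it as an outcome. Figure 1 could not be read for this review. If it shows timed recovery readings, the text must be brought into line with it.

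Finally, fixed times do not make the sessions fully comparable, because walk duration can differ. That is true, but they remove the dependence of the reading time on the dyspnea outcome.

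**Conclusion.** The concern holds as a defect in a stated measurement rule. Followed as written, end-of-recovery RPD carries no recovery information, and the paired comparison of HR, RR, BP, SpO2 and RPE is not time-matched whenever dyspnea recovery differs between sessions. That comparison can be biased or can mask a real difference.

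The direction is not known. It depends on how fast the vitals recover relative to dyspnea and on how long each walk lasted, and the documents give neither. Under the assumed HR values with readings at 3 and 5 min, reported differences run from −4.0 to +5.6 bpm. These show that the effect need not be negligible; they do not estimate it.

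The distance and duration endpoint, the walk readings and the RPD return time are not affected. This is worth correcting before data collection, but it does not threaten the study's main comparison.

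**What to change.** 1. In Section VI, for both sessions, record HR, RR, BP, SpO2, RPD and RPE at walk end and at the same few fixed elapsed times in recovery. Compare sessions at those times, and report walk duration alongside because it may differ.
2. Keep the observed RPD return time as the recovery endpoint. State one RPD polling interval for both sessions and a maximum duration, and record non-returners as longer than the maximum.
3. Do not test end-of-recovery RPD as an outcome; retain it as a record that recovery was reached.
4. Reword the Section VII recovery-parameter line so that return time applies to RPD only.
5. Reconcile Section VI with Table 1 on whether BP is recorded during the walk.

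The cost is protocol wording, a few extra CRF rows and a few more cuff readings. The subject is already seated, and RPD must already be asked repeatedly to detect its return.

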VIII. Statistical Analysis

The data analysis will be “per protocol.” Baseline patient demographics and characteristics will be summarized, and appropriate statistical testing will be performed for the continuous and categorical variables. Assuming a non-normal data distribution for this crossover study design, the non-parametric Wilcoxon Signed Rank Sum test will be performed with significance interval of 0.05 on all applicable variables. Otherwise, for the categorical variables, the Fisher’s Exact test will be performed. Data will be compared and graphed accordingly for a visual comparison with accompanied statistical notations.

IX. Risks and Discomforts

This pilot study does not present significant risk to patients, as supplemental oxygen is routinely provided to patients and the 6MWT is a standard/routine practice³³. The Treatment-as-Usual at the study sites involves the application of simple supplemental oxygen during mobilization. Use of the high flow nasal cannula therapy has no known risks and has been used in the clinical setting for approximately seventeen years without known reports of adverse events related to the administration of high nasal flows when appropriately conditioned to near body temperature and fully humidified. The literature indicates that approximately only 4 cmH₂O of distending pressure may be generated in the upper airway^{34,35} which is well below any known threshold for injury. In addition, it has been demonstrated that delivery of high flows of conditioned gas from a nasal cannula has a positive effect on airway mucosal function^{36,37}. The patients will be closely monitored as part of standard medical practice. Ambulation is implemented as part of the standard care practice for the patients included in this study.

For these reasons, we have determined that this study represents non-significant risk to the subjects, beyond the discomfort related to routine ambulation therapy.

X. Potential Benefits

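### All applicable variables are tested at an unadjusted 0.05 and marked on graphs, with no multiplicity rule and no exploratory label for secondary and tertiary results

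*Combined protocol and SAP*

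**What the plan says.** Section VIII sets one rule for the whole study: "the non-parametric Wilcoxon Signed Rank Sum test will be performed", "with significance interval of 0.05 on all applicable variables". It adds that "for the categorical variables, the Fisher’s Exact test will be performed". Results are to be "graphed accordingly for a visual comparison with accompanied statistical notations". For baseline demographics and characteristics it promises a summary and that "appropriate statistical testing will be performed for the continuous and categorical variables", without naming a contrast or a significance level.

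Section VII lists the variables:
- Primary: "Distance and duration of exercise during ambulation", which is two variables with no order or combination rule.
- Secondary: "Physiologic Parameters - SpO₂, HR, RR, BP, RPE, RPD", plus the time for dyspnea to return to baseline. RPE and RPD appear again under the Borg scores. That makes 7 distinct variables, counting blood pressure once.
- Tertiary: 5 clinician visual analogue scores.

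Table 1 has the physiologic parameters recorded in three session phases and at study end. No section says which phase or summary is analysed.

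No section gives a multiplicity adjustment, a test count or an exploratory label. Section II states a superiority hypothesis that names dyspnea, exertion, oxygenation and work of breathing. It closes by saying the endpoints will establish whatever effect HVNI has on ambulation relative to TAU. Section V sizes the study at 90% power and alpha 0.05 on a walking-distance difference. It also says the data will inform the size of a later randomised study.

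**The concern.** The hypothesis offers several routes to benefit, and the plan tests variables on each of them at the same level. Nothing ranks those variables against each other or limits what a significant result may be used for. A single marked difference in, say, SpO₂ or one clinician score could then be put forward as support for HVNI. The chance that at least one such mark appears by accident is well above 5%. In a study meant to plan a randomised trial, a chance finding could also steer the choice of endpoint for that trial.

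**Working it through.** **Plan's own figure.** The documents state no family-wise error rate, so there is none to reproduce. The sample size of 26 (Section V) is used below only as the number of pairs.

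**Inputs.**
- Level per test: 0.05 (Section VIII). Sidedness is not stated; two-sided is assumed.
- One test per endpoint (Section VII): 7 secondary + 5 tertiary = 12. Section VI collects clinician scores after both sessions, so they are taken as paired.
- By phase, counting what Section VI records in both sessions: baseline RR, HR, BP, SpO₂, RPD (5); walk HR, RR, SpO₂, RPE (4); end of recovery RR, HR, BP, SpO₂, RPD, RPE (6); recovery time (1); clinician scores (5). Total 5 + 4 + 6 + 1 + 5 = 21. Walk RPD is left out because Section VI asks for it during the walk only in the test session.
- Upper count, if all six physiologic parameters are compared in all three phases: 6 × 3 + 1 + 5 = 24.

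**Independent tests.** Chance of at least one p < 0.05 when every null is true = 1 − 0.95^k.
- k = 12: 1 − 0.95^12 = 0.460
- k = 21: 1 − 0.95^21 = 0.659
- k = 24: 1 − 0.95^24 = 0.708
- The chance first passes one half at k = 14: 1 − 0.95^13 = 0.487 and 1 − 0.95^14 = 0.512.

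**Correlated tests.** The two-sided signed-rank test was simulated with 26 pairs, the exact critical value (actual size 0.0493), equally correlated normal differences and 20,000 replicates.

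| Tests | Correlation 0.3 | 0.5 | 0.7 |
|---|---|---|---|
| 12 | 41% | 33% | 25% |
| 21 | 57% | 45% | 32% |
| 24 | 60% | 48% | 33% |

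In a separate run of 10,000 replicates, 12 tests at correlation 0.9 gave 15%, still about three times the nominal rate.

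**Expected false positives.** This is 0.05 × k whatever the correlation: 0.6 for 12 tests, 1.05 for 21 and 1.2 for 24.

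**Primary pair.** Distance and duration, each tested at 0.05 with no rule, give 1 − 0.95² = 0.0975 if independent. Limiting the significance claim to the primary endpoint is therefore not enough without a rule for the pair.

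**The case against.** The strongest reply is that this is a feasibility study, named as such throughout, whose stated use is to plan a randomised trial. Endpoints are already ranked as primary, secondary and tertiary, and the sample size rests on distance alone. Family-wise control of secondary outcomes is not normally demanded of a single-sequence pilot. Much of this stands: adjusting across every secondary variable is not needed. It does not excuse the silence on interpretation. The ranking has no consequence in Section VIII, where every applicable variable is tested at the same level, and Sections II and V use the language of showing a difference.

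A reader might also infer more than the documents support:
- **That a false positive is more likely than not.** With one test per listed secondary and tertiary endpoint the chance is below one half even under independence. With 21 or 24 tests it is below one half at correlation 0.5. Measures taken on the same subject in the same walk are probably correlated, though the documents give no value.
- **That the plan schedules 21 or more comparisons, or minute-by-minute tests.** It schedules measurements. The by-phase counts show what the unspecified time point would allow. They also treat RPD at baseline and at end of recovery as separate, although recovery is defined by RPD returning to its baseline score.
- **That every baseline variable is tested at 0.05.** The sentence on demographics names no level and no contrast. The narrower point is that each subject completes both periods, so demographics cannot differ between TAU and HVNI.

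**Conclusion.** The point holds as a defect in what the plan allows to be claimed. Unadjusted testing at 0.05 with marked graphs is the stated rule, and nothing labels the secondary and tertiary results exploratory. The chance of at least one spurious result is roughly 25-70%. The low end is 12 tests at correlation 0.7, and the high end is 21 to 24 independent tests. The range rests on an assumed test count, assumed equal correlation between 0 and 0.7, two-sided testing, and a null in which the two sessions do not differ for any reason.

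That last assumption matters. The sequence is fixed, TAU then HVNI, and unblinded. Order or expectation effects could produce significant differences that no adjustment of alpha would remove. This favours descriptive reporting over a correction applied to all variables.

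**What to change.** Amend Section VIII as follows:
1. State that a significance claim attaches only to the primary endpoint, and give a rule for its two variables. For example, test distance first at 0.05, since the sample size rests on it, and duration at 0.05 only if distance is significant.
2. Report secondary and tertiary variables as paired median differences with 95% intervals, labelled descriptive, with no significance marks on graphs.
3. Name one time point or summary for each secondary variable, so that the number of comparisons is fixed in advance.
4. Summarise demographics and history without TAU-HVNI tests.

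No data collection changes. The downside is that fewer results can be called significant. Readers can still see whether an interval excludes zero, so the descriptive label must carry through to the report. Paired estimates with intervals also suit the stated aim of planning a randomised study. The change does not deal with order effects, which need to be acknowledged separately.
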